14.9 Analysis of Safety

Safety variables will include AEs, concomitant medications, laboratory tests (haematology, chemistry and urinalysis), vital signs, and medical history. Safety variables will be analysed on the treatment population using descriptive statistics for continuous endpoints (e.g. mean, median, SD, minimum and maximum) and frequency counts with percentages for discrete endpoints.

Baseline is defined as the last available assessment prior to dosing on Week 1 Day 1 (Visit 1).

14.9.1 Adverse Events

All AEs will be coded using MedDRA, summarized by treatment arm and reported to FDA. Adverse events that begin prior to SUBLOCADE administration or after the 6 month visit will be presented separately. Only AEs occurring after SUBLOCADE administration will be included in the analysis.

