SUBOXONE Sublingual Film: A single test dose of 4 mg/1mg SUBOXONE sublingual film will be administered to subjects in the ED prior to administration of the SUBLOCADE injection to ensure no allergic reaction or hypersensitivity to buprenorphine is present. This dose was selected as the targeted population have received an opioid antagonist for the treatment of an OD and are expected to be experiencing significant withdrawal symptoms.

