3.4 Safety Assessments

Safety assessments include the proportion of subjects with AEs of the following types at any time during the treatment period: at least one AE, a drug-related AE, an SAE, a serious and drug-related AE, or an AE leading to treatment discontinuation.

Additional safety assessments include laboratory assessments, brief physical examinations, vital signs and concomitant medications.

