5.4 Initial SUBLOCADE Dosing Criteria

In order to initiate SUBLOCADE dosing the following criteria must be met:

- 1) Clinically stable (respiratory rate [RR] ≥ 12 , pulse oximetry $> 95\%$, Glasgow Coma Scale [GCS] score of 15)
- 2) No allergic reaction or hypersensitivity to SUBOXONE sublingual film.
- 3) More than 8 hours after the last dose of short acting opioid other than the SUBOXONE dose administered in the ED or at the clinic, or more than 48-72 after last dose of methadone.

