6.2 Screen Failure

A subject will be considered a screen failure if written informed consent is obtained but he/she does not meet inclusion / exclusion criteria or does not receive SUBLOCADE for another reason (example: the subject leaves prior to administration).

Subjects that screen fail may be re-screened for participation in the trial if they return to the ED, inpatient unit or outpatient treatment facility after a subsequent OD.

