9 STUDY DRUG MANAGEMENT

9.1 Description

The term ‘study treatment’ is used throughout the protocol to describe any combination of product received by the subject as per the protocol design. Study treatment may therefore refer to the individual study treatments or the combination of those study treatments.

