14.4 Analysis Populations

14.4.1 Treatment Population

The Treatment Population includes all subjects who receive at least 1 dose of study medication. This population will be used for all safety and efficacy analyses. In the safety analyses, subjects will be analysed according to treatment actually received.

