22 APPENDICES

22.1 Appendix 1 –Schedule of Events – Visit 1 (In ED, inpatient unit or Outpatient Clinic within 7 days (168 h) after OD

Procedure / Assessment	Screening Procedures (Visit 1)	Treatment Period (Visit 1)			Sublocade Dosing	Post-Sublocade dose Procedures
		Pre-Suboxone dose Procedures	Suboxone Dosing	Post-Suboxone dose Procedures		
Informed Consent	X					
Inclusion/Exclusion Criteria	X					
Demographics	X					
Medical History	X					
Brief Physical Examination	X					
Concomitant Medications Assessment	X					
Vital Signs	X					
Height/Weight/BMI	X					
Breathalyzer	X					
Urine Pregnancy Test	X ^b					
DSM-5 OUD/AUD/SUD Checklist	X					
Liver function laboratory tests (STAT)		X ^d				
COWS		X ^e		X		X
OC-VAS		X ^e		X		
Delay Discounting Task		X		X		
Opioid Demand Task		X		X		
SUBOXONE Test Dose			X ^{f,g}			
SUBLOCADE Dose					X	
PGx Sampling				X ^a		
AE Assessment		X		X ^g		X
Clinic appointment visit scheduled for next dose						X

AE = adverse event; COWS = Clinical Opiate Withdrawal Scale; MINI = Mini-International Neuropsychiatric Interview

- a. PGx samples will only be taken from subjects that consent to participate in the optional PGx sub-study.
- b. Urine pregnancy test, only for females of child-bearing potential. Results must be available and reviewed prior to Suboxone treatment.
- c. Subjects will be included in the study only after it is determined that subject meets all inclusion criteria and none of the exclusion criteria.
- d. STAT Local labs will be used for screening liver function tests. Samples must be drawn prior to dosing and will include ALT, AST and bilirubin. Abnormal liver function tests (LFTs) will be followed at clinic visits according to investigator's judgement. Liver function tests obtained for clinical reasons will also be used for research purposes if we are unable to obtain blood for research purposes. An etiological evaluation will be performed if a hepatic adverse event is suspected.
- e. The COWS and OC-VAS will be completed after consent but prior to first administration of SUBOXONE sublingual film.
- f. Day 1 SUBOXONE/SUBLOCADE Regimen includes supervised administration of 4mg/1 mg SUBOXONE sublingual film, followed by 300 mg SUBLOCADE administration.
- g. Subjects will be assessed for adverse events predose and 1-2 hours postdose depending on RASS score prior to discharge.

22.2 Appendix 2 – Treatment Clinic Schedule of Events – (Week 1 Day 2 – Week 25 Day 169)

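### Section 14.9.1 starts the AE count at SUBLOCADE, so AEs that begin in the hour after the SUBOXONE test dose fall outside the main proportions and are pooled with pre-drug events

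*Combined protocol and SAP*

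**What the plan says.** All references are to the combined protocol and SAP.

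- **Safety measure.** Section 3.4: "Safety assessments include the proportion of subjects with AEs of the following types at any time during the treatment period". The types listed are any AE, drug-related AEs, SAEs, serious drug-related AEs, and AEs leading to discontinuation.
- **Visit 1 schedule.** Appendix 1 has a column group that begins "Treatment Period (Visit 1". It covers the steps before, at and after the SUBOXONE dose, and an AE check is scheduled after the film.
- **Status of the film.** Section 9.1: "Study treatment may therefore refer to the individual study treatments or the combination of those study treatments". The film is described in 1.1.1 (Investigational Medicinal Product) and in 9.1.3.
- **Sequence.** The Synopsis sets a 1-hour wait after the film, then SUBLOCADE if there is no allergic reaction. Section 5.4 makes this a dosing condition: "No allergic reaction or hypersensitivity to SUBOXONE sublingual film". Section 1.1.2 gives the purpose of the test dose: "to ensure no allergic reaction or hypersensitivity to buprenorphine is present".
- **AE analysis.** Section 14.9.1: "Only AEs occurring after SUBLOCADE administration will be included in the analysis". The sentence before it sends AEs with onset before SUBLOCADE, or after the 6-month visit, to a separate presentation.
- **Population.** Section 14.4.1: "The Treatment Population includes all subjects who receive at least 1 dose of study medication". Section 6.2 classes a consented subject who never receives SUBLOCADE as a screen failure.

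**The concern.** The film is each subject's first buprenorphine dose in the study, given after an overdose reversed with an antagonist. The hour that follows is when the test dose is meant to reveal hypersensitivity, and when buprenorphine-precipitated withdrawal could first appear. Section 1.2 names precipitated withdrawal among the main risks, and the Synopsis makes withdrawal after SUBOXONE, as well as after SUBLOCADE, a safety assessment at Visit 1.

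The rule in 14.9.1 starts counting only after that hour. Followed exactly, it yields proportions for a narrower window than 3.4 appears to define. It also places reactions to the first dose in the same display as events that precede any study drug. What is at stake is whether the main AE table describes the regimen actually given or only its second component.

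**Working it through.** The plan states no AE rate, so there is no figure to reproduce. The check is a comparison of the rules, followed by a simple scale calculation.

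**Step 1. Where an AE goes, by time of onset.** AEs are collected from consent (10.1.1).

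| Onset | 3.4 read with Appendix 1 | 14.9.1 |
|---|---|---|
| Consent to SUBOXONE film | Unclear: the header also spans pre-film procedures | Separate display |
| Film to SUBLOCADE, about 1 hour | Inside | Same separate display |
| SUBLOCADE to the 6-month visit | Inside | Main analysis |

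The two rules disagree in the second row. No section reconciles them.

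**Step 2. Which AEs in the second row stay out of the main analysis.**

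- *Subject goes on to SUBLOCADE.* Section 5.4 does not bar dosing for withdrawal. Under 10.1.2 a change in severity is recorded as a new event, so withdrawal that changes after SUBLOCADE is counted. Withdrawal that begins in the gap and stays at the same severity is not.
- *Subject reacts allergically to the film within the hour.* Section 5.4 then rules out SUBLOCADE, so this AE cannot have onset after it. If study medication in 14.4.1 includes the film, the subject is in the denominator with no countable event. If it does not, the subject is in neither numerator nor denominator.

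**Step 3. Can the 3.4 proportion be recovered from the two displays?** Not as described. The separate display is not split at the film, so adding it to the main analysis would also bring in AEs from before any drug. For a subject given only the test dose, even appearing in that display depends on how 14.4.1 is read, since 14.9 runs the safety analyses on the Treatment Population.

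**Step 4. Does COWS fill the gap?** Only in part. It is scored before the film, between the two products and after SUBLOCADE (8.7.3, Appendix 1). But 14.9 does not list it among the safety variables, and it does not measure hypersensitivity. A scale finding becomes an AE only if it needs intervention or is judged clinically significant (10.1).

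**Step 5. Scale.** Let N be the treated subjects (about 100, section 5.1) and k the number whose only AE starts in the gap and does not change severity.

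Shortfall in the at-least-one-AE proportion = k / N.

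- k = 1: 1 / 100 = 1 percentage point.
- k from 0 to 10 (an assumed range; the documents give none): 0 to 10 percentage points.

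For a subject who reacts to the film and receives no SUBLOCADE, added to 100 who do, the test-dose hypersensitivity proportion is 1 / 101 = 1.0% among all given the film. The main analysis would show 0.

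**The case against.** The case for leaving 14.9.1 alone has real content.

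- **Nothing is suppressed.** All AEs are coded, summarized and reported, and those with onset before SUBLOCADE get their own presentation. SAEs go to the IRB and the company within 24 hours whatever the tables show (11.2.1). A reader might infer that reactions to buprenorphine vanish from the report. The documents do not support that: everything with onset after SUBLOCADE is in the main analysis, and gap AEs are shown elsewhere.
- **Treatment period is not formally defined.** A schedule header is a weak basis for an analysis window, and this one also covers pre-film steps. A SUBLOCADE-anchored reading has support: the Synopsis defines enrolment by a SUBLOCADE dose, 6.2 treats subjects without it as screen failures, and 14.9.2 measures exposure from the first injection. This stands as a limit on how firmly a contradiction can be asserted. It does not remove the problem, because neither 3.4 nor Appendix 1 states that reading, and the gap would still need a display of its own.
- **The window is short.** A reader might argue that the rule drops half of the observation, since it excludes one of two planned post-dose hours at Visit 1. But AEs are collected through the EOT visit at Day 169, and a share of observation hours is not a share of events. Any claim that the AE rate would be halved rests on invented rates.
- **Attribution.** Section 1.1.2 expects withdrawal from the antagonist at entry, so counting from the film may pick up withdrawal that buprenorphine did not cause. This is a fair cost, and a reason to split by onset.
- **Hypersensitivity reported as zero.** This holds only for reactions that prevent SUBLOCADE. A delayed reaction after the injection is counted.

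**Conclusion.** The point holds in a limited form and should be corrected. An AE that starts between the film and SUBLOCADE and does not change severity is outside the main AE proportions, although 3.4 with Appendix 1 reads as including it. It is presented separately, but in a display that does not separate first-dose reactions from events before any drug.

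The size cannot be estimated from the documents. It is about 1 percentage point for each affected subject per 100 treated, and probably modest in total because the gap is about 1 hour and severity changes are counted as new events. The rule can only remove events from the numerator. The net effect on a rate also depends on whether test-dose-only subjects are in the denominator, which 14.4.1 leaves open.

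The conclusion assumes that the film belongs to study treatment, as 1.1.1 and 9.1 indicate. If the sponsor meant the AE window to begin at SUBLOCADE, 3.4 should say so, and the inter-dose interval still needs its own table.

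**What to change.** 1. In 14.9.1, replace the last sentence with a rule that AEs starting or worsening after the first dose of study treatment (the SUBOXONE film) are included in the analysis and feed the 3.4 proportions.
2. Tabulate these AEs by onset: film to SUBLOCADE, and after SUBLOCADE. Present AEs from consent to the film separately.
3. In 14.4.1, state that the safety population is all subjects given the film, with SUBLOCADE-dosed subjects as the denominator for the second interval.
4. Keep the AE records of test-dose-only subjects in the database and listings, although 6.2 calls them screen failures.

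The cost is small: one sentence changed, one clarified, and onset columns added to a table. AEs are already collected from consent, so no new assessment is needed. The headline AE rate may rise slightly, and some antagonist-induced withdrawal may be counted. The onset split makes that visible.

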14.9.2 Extent of Exposure

The duration of treatment with SUBLOCADE, defined as the date of the last injection minus the date of first injection +28 days, will be summarized as a continuous summary.

The total number of SUBLOCADE injections will be presented as a continuous summary and a categorical summary. The number of subjects who had early surgical removal of SUBLOCADE depot will be summarized.

14.9.3 Laboratory Data

Summary statistics for absolute laboratory value will be presented.

14.9.4 Vital Signs

Summary statistics for vital signs will be presented.

14.9.5 Other Safety-Related Variables

Medical history will be coded using MedDRA and summarized by treatment group. Body weight, height and BMI will be summarized using descriptive statistics (mean, median, SD, minimum and maximum), including change from baseline.

Prior and concomitant medications will be coded using WHO-DD. Incidence (number and percent of subjects reporting the medication at least once during the study) will be summarized for all concomitant medications.

15 ETHICS AND RESPONSIBILITIES

15.1 Good Clinical Practice

The study will be carried out in accordance to the protocol and with local legal and regulatory requirements, ICH/GCP and all applicable subject privacy requirements.

15.2 Institutional Review Board/Independent Ethics Committee

The protocol, ICF(s) and any other written information and/or materials to be provided to subjects will be reviewed by an independent and appropriately constituted IRB/Independent Ethics Committee (IEC). If required by local regulations, the protocol should be re-approved by the IRB/IEC annually. The IRB/IEC must be constituted and operate in accordance with the principles and requirements of ICH/GCP.

Investigational medicinal product can only be released to the Investigator after documentation that all ethical and legal requirements for starting the study has been received by Indivior Inc. or designated representative.

15.3 Informed Consent

The Investigator or a person designated by the Investigator is to obtain written informed consent from each subject prior to entering the study. All written informed consent documents are required to have been reviewed and received a favourable opinion/approval from an IRB/IEC prior to presenting them to a potential participant.

The written informed consent process will include the review of oral and written information regarding the purpose, methods, anticipated duration and risks involved in study participation. The Investigator is to ensure that each subject is given the opportunity to ask questions and allowed time to consider the information provided. The Investigator or a person designated by the Investigator must also explain to each subject that participation is voluntary, and that consent can be withdrawn at any time and without reason. Subjects will receive a signed and dated copy of the signed ICF before any study-specific procedures are conducted.

In the event that new safety information emerges that represents a significant change in the risk/benefit assessment, the signed ICF should be updated accordingly. All subjects should be informed of the new information, provide their consent to continue in the study, and be provided with a signed and dated copy of the revised signed ICF.

15.4 Records Management

The Investigator must maintain all study related records (except for those required by local regulation to be maintained elsewhere) in a safe and secure location throughout the conduct and following the closure of the study. The records must be accessible upon request (e.g., for an IRB/IEC, Indivior Inc. or regulatory inspection) along with the facility, study personnel and supporting systems/hardware. All documents pertaining to the study, including all versions of the approved study protocol, copy of the ICF and other documents as required per local laws and

regulations (e.g., Health Insurance Portability and Accountability Act [HIPAA] documents), completed CRFs, source records (subject records, subject diaries, hospital records, laboratory records, drug accountability records, etc.), and other study-related materials will be retained in the permanent archives of the study site.

Where permitted by local laws and regulations, records may be maintained in a format other than hard copy (e.g., electronically in an electronic medical records system). The Investigator must ensure that all reproductions are an accurate legible copy of the original and that they meet necessary accessibility and retrieval standards. The Investigator must also ensure that a quality control process is in place for making reproductions and that the process has an acceptable back-up of any reproductions.

The minimum retention time for retaining study records will be in accordance with the strictest standard applicable for the study site as determined by local laws, regulations or institutional requirements. At a minimum, records will be maintained for 5 years after the end of the study.

16 MONITORING

In accordance with applicable regulations, GCP, clinical monitor(s) will periodically review all study data for accuracy and completeness as described in the Clinical Monitoring Plan.

The PI must allow the clinical monitor(s) direct access to all relevant documents and to allocate his/her time and the time of his/her staff to the clinical monitor(s) to discuss findings and any relevant issues.

Upon completion of the study, study closeout activities must be conducted in conjunction with the PI, as appropriate.

Steps to be taken to ensure the accuracy and reliability of data include the selection of qualified investigators and appropriate study centres, review of protocol procedures with the investigators and associated personnel before the study. Written instructions will be provided for study drug preparation and dosing, collection, preparation, and shipment of blood, plasma and urine samples are available in the prescribing information.

This study will be organized, performed, and reported in compliance with the protocol, Standard Operating Procedures (SOPs), working practice documents, and applicable regulations and guidelines.

This study is subject to inspections by Regulatory Authorities. If such a regulatory inspection occurs, the PI agrees to allow the regulatory inspector direct access to all relevant study documents. The PI must contact Indivior Inc. immediately if this occurs and must fully cooperate with the inspection conducted at a reasonable time in a reasonable manner.

17 AMENDMENTS

A protocol change intended to eliminate an apparent immediate hazard to subjects may be implemented immediately, provided the IRB/IEC is notified within 5 days.

Any permanent change to the protocol must be handled as a protocol amendment. The written amendment must be submitted to the IRB/IEC and the Investigator must await approval before implementing the changes. The Investigator or designated representative will submit protocol amendments to the appropriate Regulatory Authorities for approval.

If in the judgment of the IRB/IEC or the Investigator, the amendment to the protocol substantially changes the study design and/or increases the potential risk to the subject and/or has an impact on the subject's involvement as a study participant, the currently approved written ICF will require similar modification. In such cases, informed consent will be renewed for subjects enrolled in the study before continued participation, based on IRB/IEC determination.

18 STUDY REPORTS AND PUBLICATIONS

A clinical study report will be prepared following completion of the study. Study results will be published on clinicaltrials.gov and in a peer reviewed journal.

19 STUDY TERMINATION

The PI reserves the right to terminate the study at the investigator's site at any time. Should this be necessary, the PI or a specified designee will inform the appropriate Regulatory Authorities of the termination of the study and the reasons for its termination, and the PI will inform the IRB/IEC of the same. In terminating the study, the PI will assure that adequate consideration is given to the protection of the subjects' interests.

20 CONFIDENTIALITY

All subject-identifying documentation generated in this study is confidential and may not be disclosed to any persons not directly concerned with the study without written permission from the subject. However, authorized regulatory officials will be allowed full access to inspect and copy the records. All subject bodily fluids and/or other materials collected shall be used solely in accordance with this protocol and the ICF signed by the subject, unless otherwise agreed to in writing by Indivior Inc.

Each subject will be identified by initials and an assigned subject number when reporting study information to any entity outside of the study centre. Data containing subject identification will not be removed from the study centre without first redacting subject identifiers.

